1. BACKGROUND AND EARLIER EFFORTS

In patients diagnosed with Barrett's esophagus (BE) with high-grade dysplasia (HGD) esophagectomy has been recommended as a standard of care for treatment. However, esophagectomy is associated with high mortality and morbidity rates even in experienced centers, and is too invasive for those with HGD because lymph node involvement is unlikely (<5%) (1,2). With the development of surveillance programs, the number of patients with early stage disease has increased. Additionally, interest of less invasive, incisionless (endoscopic), and esophageal preservation therapies has grown (2). Currently available endoscopic techniques such as photodynamic therapy, radiofrequency ablation, endoscopic mucosal resection (EMR), and endoscopic submucosal dissection (ESD) have significant limitations including compromised histological assessment, stricture formation, sampling error leading to missed synchronous or metachronous lesions, requirement of life-time surveillance endoscopy, and subsequent interventions. To overcome these drawbacks, we have demonstrated the feasibility of transoral endoscopic circumferential long-sleeve resection (TECR) in the pre-clinical setting as both a diagnostic and therapeutic approach (3).

Removal of the entire segment of abnormal mucosa is believed to be the best approach in curing HGD. Biologic scaffold materials composed of a xenogeneic extracellular matrix (ECM) have been investigated extensively in the context of regenerative medicine for their ability to modify the default tissue healing response in the esophagus (4-6). In a pre-clinical model, critically sized, full circumferential defects could be repaired with minimal stricture formation if adjacent autologous muscle tissue was placed in direct apposition to the ECM scaffold at the time of surgery (4). A follow-up pre-clinical study of esophageal transection that was designed to reinforce the anastomosis of a "gastric pull-up" procedure showed restoration of a mature epithelium and regeneration of muscle tissue that bridged the gap between the native muscle tissue on either side of the surgical transaction site and prevented stricture (6). Most recently reported, the use of ECM has been extended to a pre-clinical model of aggressive endoscopic endomucosal resection such as that proposed for treatment of Barrett's esophagus, demonstrating that ECM successfully minimizes or prevents stricture formation by remodeling the default tissue via neo-epithelialization rather than scar formation (6).

Based on these experiences, we performed this endoscopic resection with ECM placement on 5 patients with HGD or T1a EAC, and the outcomes of these 5 patients were published (7). All patients developed mild segmental strictures, which were easily dilated and became stable quickly. During 4-24 months follow-up, restoration of normal mature squamous epithelium and return to a normal diet without significant dysphagia were reported for all patients. Two of 5 patients had a small focus of recurrent Barrett's esophagus but no recurrence of cancer was observed. Furthermore, we successfully performed anti-reflux surgery (laparoscopic fundoplication) to treat gastroesophageal reflux disease (GERD), the root cause of Barrett's esophagus, on 3 patients who had undergone this endoscopic resection, and all reflux symptoms have been eliminated without any complications (8).

Background on Investigational use of Esophageal Stent: As indicated by our previous application of this study design and supported by other literature, we believe using a fully

covered self-expanding metal stent (FCSEMS) for placement of the ECM poses minimal risk to subjects while providing the necessary, temporary support for the ECM to incorporate with the resected area (7, 9-14). Removability of such stents has been well documented in several animal and human models. One retrospective case series found that 95.3% of FCSEMS in 31 people were removed without complication while another found that 100% of stents in 24 patients were successfully removed without complication (9,10). Another retrospective study analyzed FCSEMS placement in 79 patients with benign disease. The investigators observed low incidence of stent induced ulceration and concluded removability was easily demonstrated (11). The only U.S. prospective clinical trial evaluating the safety of FCSEMS placement and removal concluded tissue reaction was common yet clinically insignificant in a majority of patients. Additionally, removal using rat-toothed forceps was deemed “very easy or easy” in 83% of cases with zero complications recorded overall (11).

In addition to our pre-clinical studies (4,5) a study conducted on 8 Yucatan pigs demonstrated a lack of tissue embedment and granulation and concluded that FCSEMS could be successfully removed without trauma (15).

Furthermore, we believe using self-expanding plastic esophageal stents for our purpose could be detrimental to a subject due to the high rate of stent migration and difficult deployment in narrow areas (9,13,16,17). Although plastic stents are currently FDA accepted for benign use with removal, we believe the potential for requiring dilation in order to deploy the stent as well as an inability to collapse the stent for removal could damage the ECM and result in increased risk to subjects.

Summary: Based on our prior research and experience with TECR and ECM placement, we propose to utilize this novel technique as an alternate treatment for patients with esophageal High Grade Dysplasia. This esophageal-preserving approach is externally incisionless and less invasive, whereas the current standard of care, esophagectomy, is highly invasive and may be too aggressive a treatment for those with HGD.

Endoscopic circumferential esophageal resection could be a one-step therapeutic approach to removing dysplastic tissue. ECM is a promising material to promote reconstitution of the resected esophageal epithelium; potentially preventing or minimizing stricture formation for advanced dysplasia. This combined approach could successfully treat patients, preserve the esophagus, reduce incidence of stricture formation, and result in less morbidity and mortality. The results of this study will potentially change the current approach to treat patients with HGD. The outcomes of this feasibility study could also lay the groundwork for future studies utilizing this approach to treat more advanced T1a esophageal adenocarcinoma patients.

2. PURPOSE

Evaluate the safety and efficacy of transoral endoscopic esophageal circumferential resection (TECR) with ECM placement for the treatment of BE with High-Grade Dysplasia (HGD).

2.1 Primary Objectives

2.1.1 Primary Efficacy Objectives

1. To evaluate incidence of stricture formation requiring dilation ($\geq 30\%$ luminal diameter reduction with dysphagia) following TECR with ECM placement. Evidence of stricture formation will be confirmed endoscopically at 2 weeks, and endoscopically and through barium swallow at Month 1, Month 3, Month 6, Month 9, and Month 12 post procedure, and the proportion of subjects with and without stricture formation at the trial endpoints will be compared to historical data.
2. To evaluate incidence of recurrence of BE with HGD through 12 months following TECR with ECM placement. Incidence of disease recurrence will be confirmed endoscopically with pathology confirmed biopsies at 2 weeks, Month 1, Month 3, Month 6, Month 9, and Month 12 post procedure, and the proportion of subjects with and without disease recurrence at the trial endpoints will be compared to historical data.

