3.4.9.1.1 Histological Evaluation of Tissue Biopsy

All biopsy tissue samples collected during EGD will be sent to a board certified pathologist employed by the Allegheny Health Network for evaluation and final post-operative diagnosis. The pathologist will visually analyze the biopsy sample to classify the tissue into dysplastic grades. Potential subjects for this study will not be approached to consent until a pathology report is provided to the PI. This report is typically made available to physicians within one week of sample collection. Only patients with tissue grades (HGD) who meet the study inclusion criteria are eligible for this study.

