3.4.10.1 TECR

TECR will be performed to resect the entire length and area of the BE lesion in the in-patient setting. A dissection plane between the mucosal and submucosal layer will be created by injection of sodium hyaluronate (SH) (HYALGAN®, Bridgewater, NJ) mixed with indigo carmine and epinephrine into a site immediately distal to the gastroesophageal junction. This site will represent the “goal” or terminus of therapeutic endoscopic mucosal resection (EMR). The normal esophageal mucosa 1cm proximal to the squamocolumnar junction will represent the “entry” or beginning of resection. Circumferential esophageal mucosal resection will then be performed at both of these sites thereby defining the proximal and distal resection margins. More SH will be injected and endoscopic mucosal resection with a needle knife (Olympus America Inc., Center Valley, PA) will be performed to create a submucosal tunnel along the entire length of the longest lesion. The bridging vessels between the mucosal and submucosal layer will be cauterized using hemostat forceps. The creation of 2-3 additional submucosal tunnels between the proximal and distal resection margins will be created leaving the attachments between each tunnel for counter-traction. At the proximal entry point, a circumferential cuff of mucosal tissue will then be developed using standard cap resection, cautery dissection, and/or hydro-dissection with irrigation catheter techniques. Using EMR technique, the remaining attachments will be dissected away from the submucosal later thereby freeing the entire sleeve of tissue. The specimen will then be retrieved through the mouth. Hemorrhage within the submucosal tube will be controlled and the endoscope will be removed.

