3.4.12 Adverse Events (AE)

An adverse event is defined as any untoward or unfavorable medical occurrence in a human subject, including any abnormal sign (for example, abnormal physical exam or laboratory finding), symptom, or disease, temporally (timing of) associated with the subject's participation in the research, whether or not considered related to the subject's participation in the research.

An underlying disease that was present at the time of enrollment is not reportable. However, any increase in the severity or seriousness of the underlying disease is to be reported as an adverse event.

Events meeting the definition of an AE include:

- Exacerbation of a chronic or intermittent pre-existing condition including either an increase in frequency and/or intensity of the condition.
- New conditions detected or diagnosed after investigational product administration even though it may have been present prior to the start of the study.
- Signs, symptoms, or the clinical sequelae of a suspected interaction.

The following list includes, but is not limited to, events that will be considered adverse events for this study:

- 1) stent migration,
- 2) perforation,
- 3) severe pain,
- 4) bleeding,
- 5) fever,
- 6) reflux,
- 7) aspiration and
- 8) severe stricture formation refractory to dilation

Events that do not meet the definition of an AE include:

- Medical or surgical procedure (e.g., endoscopy, appendectomy); the condition leading to the procedure is an AE.
- Situations where an untoward medical occurrence did not occur (social and/or convenience admission to a hospital).
- Anticipated day-to-day fluctuations of pre-existing disease(s) or condition(s) present or detected at the start of the study that do not worsen.
- The disease/disorder being studied or expected progression, signs, or symptoms of the disease/disorder being studied, unless more severe than expected for the subject's condition.

All adverse events will be assessed and coded in accordance with CTCAE 4.0. Adverse events will be documented through a subject specific AE log and AE CRF.

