5.1.1.1 Parameter of Interest

The parameter of interest is the percent of subjects with stricture formation.

5.1.2 *Primary Efficacy Objective 2*

To record incidence of recurrence of BE with HGD through 12 months following TECR with ECM placement. Incidence of disease recurrence will be confirmed endoscopically with pathology reviewed biopsies at 2 weeks, Month 1, Month 3, Month 6, Month 9, and Month 12 post procedure, and the proportion of subjects with and without disease recurrence at the trial endpoints will be compared to historical data.

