5.1.2.1 Parameter of Interest

The parameter of interest is the percent of subjects with recurrence of BE.

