5.5.1 Future General Statistical Methods

All patients that undergo TECR with ECM placement for treatment of BE with HGD and/or superficial (T1a) EAC during the study period will be included in the analysis. There are two primary efficacy endpoints: the proportion of patients with stricture formation requiring dilatation ($\geq 30\%$ reduction in esophageal luminal diameter) and the proportion of recurrence of BE with HGD and/or superficial (T1a) EAC during the 12 months post initial procedure. The primary safety endpoints will be the proportion of patients experiencing either a serious system or procedural adverse event during the 2 week post initial procedure period or any study related adverse event occurring during the 12 months post initial procedure period.

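### Objective 2 omits adenocarcinoma, names two different events, and counts Week 2 high-grade dysplasia as recurrence with no prior clear biopsy

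*Combined protocol and SAP*

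**What the plan says.** Section 2.1.1 sets the second primary efficacy objective as "To evaluate incidence of recurrence of BE with HGD through 12 months following TECR with ECM placement". It lists the biopsies that count: "Incidence of disease recurrence will be confirmed endoscopically with pathology confirmed biopsies at 2 weeks, Month 1, Month 3, Month 6, Month 9, and Month" (the list closes with the 12-month visit). Section 5.1.2 keeps the same event and visits: "To record incidence of recurrence of BE with HGD through 12 months following TECR with ECM placement". Section 5.1.2.1 then drops the HGD qualifier: "The parameter of interest is the percent of subjects with recurrence of BE".

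Section 3.3 puts the Week 2 visit at 14 days, plus or minus 4. Section 3.4.10.1 gives the aim of the resection as removal of the whole BE lesion. No section defines recurrence, asks for a negative biopsy first, or defines residual disease.

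Adenocarcinoma enters the efficacy event only in 5.5.1, as "the proportion of recurrence of BE with HGD and/or superficial (T1a) EAC during the 12 months post initial procedure". Section 5.5 presents that text as a possible future analysis for 30 or more subjects, so it does not govern the ten-subject study.

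**The concern.** The objective should tell the reader whether one resection clears HGD and whether neoplasia is found again within 12 months. Three features get in the way.

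- **Adenocarcinoma is not an event in 2.1.1 or 5.1.2.** Cancer at baseline makes a patient ineligible (3.2.2, 3.4.9.2), so adenocarcinoma on a follow-up biopsy would be new or previously undetected disease. It is the worst efficacy outcome, and if HGD is absent from the biopsy the subject is counted on the favourable side.
- **The event changes between sections.** BE with HGD and BE of any grade are different endpoints and can give different rates from the same biopsies.
- **Persistence and recurrence share one label.** HGD found 10 to 18 days after an intended complete resection more plausibly reflects tissue left behind than disease that returned. The plan has no rule to tell the two apart, so the recurrence percentage may mix incomplete resection with later reappearance.

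**Working it through.** **Inputs.** N = 10 (5.4). Week 2 window: 14 − 4 = Day 10 to 14 + 4 = Day 18 (3.3). The plan gives no target rate, alpha or power for Objective 2, and section 5 says ten subjects are too few for a comprehensive analysis, so there is no stated figure to reproduce.

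**Each finding under each wording** (last column: the definition proposed under the fix):

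| Follow-up biopsy | 2.1.1 and 5.1.2 | 5.1.2.1 | Proposed |
|---|---|---|---|
| HGD at Week 2 | Recurrence | Recurrence | Failure, shown as residual/persistent |
| HGD first found later, Week 2 negative | Recurrence | Recurrence | Failure, shown as found after a negative biopsy |
| Adenocarcinoma, no HGD, BE present | No event | Recurrence of BE | Failure, adenocarcinoma also shown alone |
| Adenocarcinoma, no HGD, no BE | No event | No event | Failure, adenocarcinoma also shown alone |
| BE without HGD | No event | Recurrence | Not failure, shown separately |

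The two current wordings disagree in the third and fifth rows. Neither identifies cancer as cancer.

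**The inconsistency in the pilot data.** Section 1 reports that 2 of 5 earlier patients had a focus of recurrent BE and none had recurrent cancer. The HGD status of the two is not given. Under 5.1.2.1 that is 2/5 = 40% (exact 95% interval 5.3 to 85.3%). Under 2.1.1 it could be anything from 0/5 to 2/5.

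**Worked example (all counts assumed).** Two subjects have HGD at Week 2, one has HGD later, one later has adenocarcinoma only, and six have no finding.

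- 2.1.1 and 5.1.2: (2 + 1)/10 = 3/10 = 30% (exact 95% interval 6.7 to 65.2%).
- 5.1.2.1: 3/10, or 4/10 if the adenocarcinoma biopsy also shows BE.
- Proposed failure: (2 + 1 + 1)/10 = 4/10 = 40% (12.2 to 73.8%).
- Difference between the first and the last: 4/10 − 3/10 = 1/10, or 10 points, all from the adenocarcinoma case.
- Split: Week 2 positive 2/10 = 20%. First found after a negative Week 2 biopsy (1 + 1)/(10 − 2) = 2/8 = 25%, of which HGD 1/8. Adenocarcinoma 1/10.

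The two Week 2 positives are failures under every column. Separating them alters the label and the recurrence figure (3/10 against 2/8) and leaves their contribution to total failure unchanged.

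**Smallest case.** If the only positive subject has adenocarcinoma without HGD, 2.1.1 reports 0/10 (exact 95% interval 0 to 30.8%). The proposed event gives 1/10 (0.3 to 44.5%).

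**How often the Week 2 label would matter.** The documents give no rate. With an assumed chance p per subject of HGD at Week 2, the chance of at least one among ten is 1 − (1 − p)^10:

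| Assumed p | At least one of 10 |
|---|---|
| 5% | 40% |
| 10% | 65% |
| 20% | 89% |
| 30% | 97% |

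**The case against.** The best defence is that this is a descriptive feasibility study in ten people with biopsies recorded by visit. Anyone can list the Week 2 positives afterwards, and the 12-month count can be read as treatment failure. For Week 2 HGD that largely stands: the issue is the label and the recurrence rate, and a reader who infers that each such subject shifts total failure by 10 points would be wrong. It does not help the adenocarcinoma-only subject, whom the stated event leaves out.

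A reader might also infer that cancer could go unreported altogether, because 3.4.12 removes from the adverse events "The disease/disorder being studied or expected progression, signs, or symptoms of the disease/disorder being studied" unless more severe than expected. The documents do not support so strong a reading. The same section makes worsening of the underlying disease, and conditions newly diagnosed after treatment, reportable, and 5.6 summarises all-cause adverse events. The section pulls both ways, and capture there would not correct the efficacy endpoint in any case.

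A third tempting inference is that the resected sleeve never reaches pathology. Section 3.4.10.1 ends with "The specimen will then be retrieved through the mouth". Section 3.4.9.1.1 speaks of biopsies: "All biopsy tissue samples collected during EGD will be sent to a board certified pathologist". The Day 0 row in section 4 lists no histology. That is silence, not evidence that examination is omitted: the case report forms (Appendix 11.4) are not in the text available, and section 1 describes the technique as diagnostic as well as therapeutic.

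Finally, a mismatch with the historical comparator cannot be demonstrated. No historical recurrence rate is given; the 41% in 5.5.4 is for stricture.

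**Conclusion.** The point holds for the ten-subject study. The event in 2.1.1 and 5.1.2 leaves out adenocarcinoma without HGD, 5.1.2.1 names a different event, and Week 2 HGD is called recurrence without prior clearance. Section 5.5.1 does not cure this: it depends on expansion and adds only T1a disease.

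Each adenocarcinoma-only subject changes the failure proportion by 10 percentage points. The Week 2 issue affects labelling and the recurrence rate only. Describing Week 2 HGD as incomplete resection is an inference from the short interval and the intended complete removal; the documents establish only that no rule separates the two. The example counts and the per-subject rates are assumptions. This should be corrected before results are reported, because in a series this small accurate classification is most of what the study can deliver.

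**What to change.** Use one event in 2.1.1, 5.1.2 and 5.1.2.1: HGD or any adenocarcinoma on a scheduled post-procedure biopsy through Month 12, named treatment failure. Report separately, from the same biopsies:

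- (a) HGD or adenocarcinoma at the first post-resection (Week 2) biopsy, labelled residual/persistent disease;
- (b) HGD or adenocarcinoma first found after a negative biopsy, with a note that one negative Week 2 biopsy does not prove clearance;
- (c) adenocarcinoma on its own;
- (d) BE without HGD.

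If the resected specimen is examined in routine care, record its worst grade and margin status as descriptive data to help interpret (a). It should not be a failure criterion.

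The cost is endpoint wording, one summary table and, where a pathology report exists, a few case report form fields. No biopsy or visit is added. The downside is that the reported failure rate may look slightly worse.

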2.1.2 Primary Safety Objectives

1. To demonstrate the acute safety of TECR with ECM placement for treatment of BE with HGD by evaluating all serious system and procedure related adverse events occurring in the first 2 weeks post procedure.
2. To demonstrate the long-term safety of TECR with ECM placement for treatment of BE with HGD by evaluating all study related adverse events occurring more than 2 weeks post procedure through 12 months post procedure.

2.2 Secondary Objectives

1. To record the incidence of stent migration at 2 weeks post procedure. Stent migration will be determined endoscopically, and defined as any movement from initial deployment location greater than 1cm.
2. To record incidences of poor stent integrity during removal (e.g. stent fracture).
3. To record the number of subsequent follow up treatment interventions (aside from study-related follow up time points) required post-procedure through 12 months.

2.3 Other Data Collected

The following data will be collected and summary observations will be compiled:

- Medical History and Demographics
- Clinical Data
 - Physical Examination

- Vital Signs
- Positron Emission Tomography/Computed Tomography (PET/CT) Scan
- Endoscopic Ultrasound (EUS)
- Barium Swallow Test (BaSW)
- Upper Endoscopy (EGD) with biopsy
- Upper Endoscopy (EGD) photos of inside of esophagus
- Endoscopic Mucosal Resection (EMR) for tissue grading
- Chest X-ray (may be required)
- Electrocardiogram (ECG) (may be required)
- Pulmonary Function Test (PFT) (may be required)
- Blood Testing (CBC, platelet count, chemistry, and electrolyte panel)
- Balloon Dilatation frequency and outcomes
- Subject Questionnaires
 - Dysphagia Severity Questionnaire
 - General Quality of Life as Assessed by the SF-36
 - GERD-HRQL
- TECR with ECM Placement Procedure Data
 - Mapping and Dimensions of Esophageal Segment to be Removed
 - ECM Device Size Information
 - Final Mapping and Location of ECM Placement
 - Stent size and associated information

